## 7 STUDY PROCEDURES AND EVALUATIONS

### 7.1 Screening

A separate Screening Visit (Visit 1) may be performed when a washout period is required or for scheduling purposes. Alternatively, Visits 1 (Screening) and 2 (Baseline/Day 1) may be combined if no washout period is required. The subject number, date of visit, date of informed consent, reason for screen failure (if applicable) and study status will be captured in the eCRF for every screen failure subject. The Baseline/Day 1 (Visit 2) Visit must occur no later than 60 days after the Screening Visit. Medical history should be collected for the prior 1 year period and concomitant medications, therapies, and procedures collected for the prior 6-month period. Only ongoing medical conditions and ongoing concomitant medications should be entered into the eCRF.

A screen failure is a subject who received information about the study, including signing an informed consent and possibly performing some study-related procedures, but was not randomized and/or did not use study product.

## 7.2 Demographic and Baseline Characteristics

Demographic variables include age (computed from date of birth and Baseline Visit date), race, ethnicity, weight, height and sex.

## 7.3 Efficacy Variables

### Definition of the treatment area

Prior to the first application of the study medication at Visit 2, the Investigator will define the treatment area. The subject must have 5 or more AK lesions within a single contiguous 5 cm x 5 cm (25 cm^2) area of the face and/or scalp. Only a single 25 cm^2 area will be treated per subject. If the subject has extensive lesions in an area spread over the face and scalp, the lesional area on the face will be preferably selected for treatment. In order to determine and identify the position of the treatment area at each Visit, a plastic grid foil will be laid on the treatment area(s) and the contours of the treatment area(s) will be circumscribed. The lesions in the area will be circumscribed as well. Furthermore, facial features like eyebrows, ears, etc. will be circumscribed and marked. The foil will be labelled with the subject number and filed in the source document. It will be used again at Visits 3 to 6 (EOS).

The subject will need to be instructed where the treatment area is located. For this purpose, the Investigator will insert a drawing into the diary depicting the location of the treatment area. Subjects will be instructed to apply the study product to the entire area as defined by this drawing.

### Efficacy assessment

The treated area will be inspected visually and by palpation. This will always be done by the same Investigator at each investigational site (unless the Investigator has delegated it to a trained designee, with proper documentation). The number of AK lesions being either visible or palpable in the defined treatment area will be assessed at all study visits. All lesions in the treatment area will be included in the lesion count even if the lesion is a new lesion that was not identified during the first Visit.

## 7.4 Safety Variables

Safety assessments include physical examinations (HEENT, lungs, heart, abdomen, skin, neurologic), vital signs (blood pressure, pulse rate), 12-lead EKGs, hematology/chemistry/urinalysis laboratory tests (Appendix 2), urine pregnancy tests for women of child bearing potential, local tolerability evaluation of the treated skin (including erythema, edema, weeping/exudate, flaking/scaling/dryness, scabbing/crusting, erosion/ulceration, vesiculation/blistering), and collection of adverse events (AEs) data. Adverse events will be collected by spontaneous reports from subject, either verbal or recorded in the subject diary, by directed questioning of subject, and by observation (see [Section 8](#) for details about AEs). For female subjects of child bearing potential, urine pregnancy tests will be conducted at Screening, Baseline, and every subsequent visit. The test must have a sensitivity of at least 25 mIU/mL for human chorionic gonadotropin.

Adverse events, whether believed by the Investigator to be related or unrelated to treatment, will be recorded on the CRF.

## 7.5 Drug Concentration Measurements

Study drug concentration measurements will not be conducted in this study.

## 7.6 Early Withdrawal of Subjects

1. Subjects should be withdrawn from the study if they no longer wish to participate, are being uncooperative, or if the Investigator feels that it is in the best interest of the subject to withdraw.
2. Subjects with protocol deviations or for whom it is discovered should have been excluded should not be withdrawn unless there is a safety concern. The protocol deviation should be recorded in the subject's source documents and the eCRF.
3. If during the course of treatment a subject experiences a cardiovascular or hematologic AE (including abnormal laboratory values) of Common Terminology Criteria for Adverse Events (CTCAE) Version 4.02 Grade 2 or higher, the study product will be discontinued and the subject will be withdrawn from the study.
4. Subjects who experience an AE resulting in or requiring discontinuation of study product use should be encouraged to be followed until the AE is resolved or stabilized.
5. If a female subject becomes pregnant during the study, study product will be discontinued immediately and she will be followed through the pregnancy and delivery. Details of the pregnancy, delivery and health of the infant should be recorded on the Pregnancy Surveillance Form. The Sponsor will be notified immediately after the subject is detected to be pregnant.
6. At the time of study discontinuation, the Investigator will record the reason for early withdrawal, date of last study product application, date of last visit or contact, collect adverse event data, and, if possible, perform all End of Study Visit specific evaluations. Every attempt should be made to contact subjects who are lost-to-follow-up. At least three attempts must be documented in the subject's source document, including the use of at least one certified letter. Any contact, either direct or indirect, should be made with the purpose to document the final status of the subject with regard to safety. Subjects who withdraw early will not be replaced.

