### 3.1 Primary Efficacy Endpoint:

The proportion of subjects with complete clearance of AK lesions at the End of Study Visit, at 16 weeks (absence of clinically visible or palpable AK lesions in the treatment area) for DFD-07 (celecoxib) Cream, 2.5% BID compared to Vehicle Cream.

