### 6.6.2 Unblinding

This is a double-blind study so neither Investigator nor subject will know which medication they receive. DFD-07 (celecoxib) Cream, 1.25% and 2.5%, and its matching Vehicle for DFD-07 Cream will be similar in appearance and have identical packaging.

The blind should be broken for all subjects suffering serious adverse events (SAEs) in which knowledge of the treatment assignment is critical to the subject's management. The blind for the subject may be broken by the Investigator, or designee, by contacting the IWRS. The blind should not be broken at the study site level except in a medical emergency (where knowledge of the study medication received would affect the treatment of the emergency). For a medical emergency, the blind must only be broken following discussion with Sponsor medical monitor, on a case-by-case basis, at the discretion of the Investigator/treating physician/Sponsor.

If the blind is broken, the date, time, and reason must be recorded in the subject's source record, eCRF, and any associated adverse event (AE) report. If an Investigator, site personnel performing assessments, or subject is unblinded, the unblinding incident and unblinded subject must be listed as a major protocol deviation. A subject for whom the blind is broken will discontinue study medication and be scheduled for an End of Study safety follow-up visit and then discontinued from the study. The subject will be encouraged to stay in the study until the AE is resolved or stabilized. All Investigators and the IRB will receive blinded safety reports. However, on the request of the IRB, the Sponsor will send unblinded reports directly to the IRB.

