## 11.2 Analysis Data Set

### 11.2.1 Intent to Treat

The intent-to-treat population (ITT) will be the primary efficacy analysis data set and consists of all subjects who are randomized and dispensed study medication.

Missing data for efficacy analysis will be replaced using last observation carried forward (LOCF). If a subject withdraws early from the study, that subject's efficacy assessments captured at the early termination visit will be assigned to the nearest corresponding scheduled visit that has been missed.

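### Two protocol rules (7.6 item 3 and unblinding) end study participation along with study product, so the Week 16 primary outcome of these subjects is imputed rather than observed; keeping them for the Week 16 count is a cheap improvement

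*Protocol*

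**What the plan says.** The primary endpoint in Protocol 3.1 is "complete clearance of AK lesions at the End of Study Visit, at 16 weeks", for 2.5% BID against Vehicle. Protocol 11.2.1 and SAP 2.2 analyse it in all subjects randomized and dispensed product.

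Two rules end study participation together with product:

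- **Protocol 7.6 item 3.** For a cardiovascular or hematologic AE (abnormal laboratory values included) of CTCAE Grade 2 or higher during treatment, "the study product will be discontinued and the subject will be withdrawn from the study". The rule does not depend on causality.
- **Protocol 6.6.2.** A subject whose blind is broken "will discontinue study medication and be scheduled for an End of Study safety follow-up visit and then discontinued from the study". The timing of that visit is not given.

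Two other rules stop product without stating that the subject leaves the study. Under 7.6 item 4, subjects with any other AE that stops product "should be encouraged to be followed until the AE is resolved or stabilized". Under item 5 (pregnancy), "study product will be discontinued immediately and she will be followed through the pregnancy and delivery". Neither asks for a Week 16 lesion count.

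Some data are collected on exit. Under 7.6 item 6 the Investigator should, at discontinuation, "if possible, perform all End of Study Visit specific evaluations", and 7.10.7 includes a lesion count among the early-withdrawal procedures. Protocol 11.2.1 assigns that assessment to the nearest scheduled visit that was missed, and fills other gaps in the ITT set by LOCF. For the per-protocol set, Protocol 11.2.2 and SAP 2.2 instead score discontinuation for lack of efficacy, worsening or a treatment-related AE as failure at later visits. In SAP 4.1, the partial-clearance and percent-change tables are labelled LOCF or multiple imputation; the complete-clearance tables carry no such label.

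**The concern.** Stopping product and stopping outcome collection are separate decisions. An intent-to-treat comparison at Week 16 needs the Week 16 status of every randomized subject, including those no longer on product. These two rules end that collection, and a different quantity fills the gap: a count made on treatment or just after stopping, not one made at the end of the four-week treatment-free period.

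The substitute can err either way. An early count may miss clearance that came later, and a clear count at withdrawal may hide a recurrence before Week 16. Item 3 is triggered by events after randomization, so the number of removals could differ between arms. The imputation would then bear on the treatment comparison itself.

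**Working it through.** **1. What stands in for Week 16.** Laboratory tests and EKGs are scheduled at Baseline, Week 4 and Week 12 (Study Schedule). An item 3 event found and acted on at Week 4 leaves a count 16 − 4 = 12 weeks before the endpoint. One found at Week 12 leaves a count 16 − 12 = 4 weeks before it. In the second case the nearest missed visit is Week 16, so that count is entered as the Week 16 value. In the first it reaches Week 16 by being carried forward. After unblinding the gap cannot be stated, because the visit has no timing.

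**2. The plan's own sample size.** Inputs from Protocol 11.1 and SAP 2.8: 45% against 20%, power 80%, α 0.05, 10% drop-out. With pooled variance, two-sided, mean rate 0.325:

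n = [1.960 × √(2 × 0.325 × 0.675) + 0.842 × √(0.45 × 0.55 + 0.20 × 0.80)]² / 0.25² = 53.9, so 54 per arm; 54 / 0.90 = 60.

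Both stated figures reproduce. The 54 requires a two-sided test; one-sided gives 43. So two-sided 0.05 is used below, although the hypotheses in Protocol 11.4 and SAP 2.6 are directional.

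**3. Effect on power.** Let w be the share of an arm removed under the two rules. The documents do not give it, so it is assumed. If every removed subject is scored as not cleared, and would otherwise have cleared at the arm's rate, the analysed rate is p × (1 − w). Exact power is the sum of the binomial probabilities of all outcomes at 60 per arm that Pearson's chi-square rejects.

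| Removed, active / Vehicle | Analysed rates | Exact power |
|---|---|---|
| 0 / 0 | 45.0% / 20.0% | 84.8% |
| 1% / 1% | 44.55% / 19.8% | 84.3% |
| 2% / 2% | 44.1% / 19.6% | 83.8% |
| 5% / 5% | 42.75% / 19.0% | 82.2% |
| 5% / 0 | 42.75% / 20.0% | 78.3% |

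The SAP's switch to Fisher's exact test when a cell is below 5 leaves these figures unchanged. In subjects, 1% to 2% of 60 is 0.6 to 1.2 per arm, and 5% is 3.

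**4. LOCF instead of failure scoring.** If the carried-forward count shows clearance at a fraction f of the Week 16 rate, the analysed rate is p × (1 − w + w × f). Failure scoring is f = 0, and f = 1 gives no loss. With w = 10% per arm and f = 0.5, the rates are 45% × 0.95 = 42.75% and 20% × 0.95 = 19.0%, the same as the 5% / 5% row. For f between 0 and 1, the table is therefore the pessimistic end for a given share removed.

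**5. Passages that do not agree.** Section 6.6.2 has the unblinded subject discontinued from the study, yet encouraged to stay until the AE resolves or stabilizes. It also classes unblinding as a major protocol deviation, while 7.6 item 2 says subjects with deviations should not be withdrawn unless there is a safety concern.

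**The case against.** **Scope.** A reader might infer that anyone who stops product under any rule leaves the study. The documents do not say so: only item 3 and unblinding join the two. Items 4 and 5 are silent on study withdrawal, and item 2 keeps subjects with deviations in.

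**Cause.** It is tempting to say that these withdrawals are treatment-related and so must vary with dose. Item 3 applies whatever the cause, and unblinding turns on medical need. Local skin reactions, whose Severe grade in Protocol 8.2 is defined by stopping product, fall under item 4. The animal studies in the Introduction report no celecoxib-related systemic effects. A difference between arms is possible, not shown.

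**Existing provisions.** The ITT value is not left blank: there is an exit count, a mapping rule and LOCF. That is so, but the count belongs to another time point.

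**Size.** Applying the 10% drop-out to both arms with failure scoring gives 79.3%, and 15% on active against 5% on Vehicle gives 66.3%. Neither measures this point. The 10% covers drop-out from all causes, including loss to follow-up and refusal, which retention wording cannot recover. The 15%/5% split has no source in the documents. The ITT rule in Protocol 11.2.1 is LOCF; failure scoring is a per-protocol rule.

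**The remedy.** After unblinding, the Investigator who normally counts the lesions (Protocol 7.3) may know the allocation, so the retained count may be an unblinded assessment by inspection and palpation. This stands, and the fix has to deal with it.

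Finally, Protocol 11.1 describes the trial as having an exploratory dose-response character, so this is an improvement rather than the correction of an error. That also stands.

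**Conclusion.** The point holds for 7.6 item 3 and for 6.6.2, and only there. For those subjects the protocol ends collection of the Week 16 outcome and relies on a count from an earlier or unspecified time. The likely cost in power is small: about one percentage point at most for 1% to 2% removed per arm, even under failure scoring. It falls below the planned 80% in the scenario with 5% lost on active and none on Vehicle. These figures rest on assumed removal shares, the planned 45% and 20%, a two-sided 0.05 test, and removed subjects otherwise clearing at their arm's rate.

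The case for change is less bias and less dependence on imputation in the primary comparison. It is a cheap improvement; nothing here invalidates the trial.

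**What to change.** Leave the rules for stopping product as they are. In Protocol 7.6 and 6.6.2, state that a subject who stops product is asked to remain for the outstanding visits, at least the Week 16 lesion count, unless consent is withdrawn. State in Protocol 11.2.1 and SAP 2.2 that this observed count is used in the ITT analysis.

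Flag any count made by an unblinded assessor. Where a site already has a trained designee who is still blinded, have that person count; Protocol 7.3 allows documented delegation. Add a sensitivity analysis without the unblinded counts.

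Reconcile 6.6.2 (discontinued from the study, yet encouraged to stay; unblinding a major deviation) with 7.6 item 2 (deviations alone do not lead to withdrawal).

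The cost is protocol and SAP wording, plus a few visits that are already in the schedule. Some subjects will decline, and a few of the counts gained may be unblinded.

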## 7.7 Modification of Protocol

No amendments to this protocol can be made without consultation with and agreement of the Sponsor, and IRB. Amendments must be made in writing. Modifications needed for the safety of subjects will be made immediately with notifications made as soon as possible.

## 7.8 Early Termination of Study

If it is determined by the Sponsor or Investigators that the study presents an unreasonable and significant risk to subjects, the study will be terminated as soon as possible, and in no event later than 5 working days following the determination that the study should be discontinued. The IRB and FDA must be notified as soon as possible about early termination of the study due to safety concerns.

## 7.9 Data Safety Monitoring Board

A Data Safety Monitoring Board will not be utilized in this study.

## 7.10 Study Schedule

A Study Schedule Chart can be found on page 9. There are at least 5 study visits; Screening (Visit 1), Baseline (Visit 2, Day 1), Week 4 (Visit 3), Week 8 (Visit 4), Week 12 (Visit 5-End of Treatment) and 4 Weeks Post-Treatment (Visit 6 – End of Study). The Screening Visit and Baseline/Day 1 Visit may be combined into a single visit if no wash-out is required. The visit window is  $\pm 5$  days for Weeks 4, 8, 12 and 16. Visits 1 and 2 cannot be separated by more than 60 days.

### 7.10.1 Visit 1 - Screening Visit

The Screening Visit should occur no more than 60 days before the Baseline Visit.

1. Obtain written informed consent prior to initiating any study procedures or before withdrawing any of the therapies prohibited during the study (including the wash-out period, if needed). Provide subject with signed copy of consent form. Document informed consent in the subject's study record.
2. List the subject on the Screening/Enrollment Log and assign a subject number. Subject numbers consist of the 2-digit site number followed by sequential 3-digit numbers usually starting with 001 (e.g., 01-001, 01-002 etc.). All subjects including screen failures should be assigned a subject number.
3. Perform a urine pregnancy test on all female subjects of child bearing potential.
4. Collect demographic data – date of birth, sex, race, ethnicity, height and weight. Review and record medical history, AK history (including naïve vs previous therapy, AK treatment received 12 months prior to screening, onset date for AK and first AK treatment), and concomitant medications, therapies, and procedures. Medical history (including any cosmetic or therapeutic procedures, such as laser, peeling, and photodynamic therapy, within 2 cm of the selected treatment area and within the 2 weeks prior to the Baseline Visit) and AK history should be collected for the prior 1-year period and concomitant medications, therapies, and procedures collected from the prior 6-month period. Only ongoing medical history items and ongoing concomitant medications should be entered on the eCRF. AK history will be collected and recorded in the eCRF.
5. Assess AK lesions (counting the visible and palpable lesions and measuring total area of lesions) to confirm that the subject has a single contiguous 5cm x 5cm area that qualifies for treatment on the face and/or scalp. If the subject has extensive lesions in an area spread over the face and scalp, the lesional area on the face will be preferably selected for treatment.
6. Documentation of size and location of selected treatment area on grid foil
7. Collect vital signs (blood pressure and pulse rate).
8. Screen subjects according to the study inclusion/exclusion criteria to determine tentative eligibility. Initiate any protocol-required washout, if applicable.
9. Schedule Visit 2 (Baseline/Day 1). If no washout is required, Visit 1 and Visit 2 may be combined.

### 7.10.2 Visit 2 - Day 1 - Baseline Visit

If no washout is required, Screening and Baseline may occur on the same day.

1. Update the medical history and concomitant medications. Any medical event (not related to a protocol intervention) that occurred since informed consent form was signed should be recorded as medical history. Only ongoing medical conditions and ongoing concomitant medications should be entered on the eCRF.
2. Collect data on AEs. Any new medical event or need for medication caused by a protocol procedure performed at the Screening Visit should be considered an AE except for worsening AK.
3. Confirm eligibility according to inclusion/exclusion criteria.
4. Collect blood (2/3 tablespoon) and urine for hematology/chemistry/urinalysis safety labs.
5. Conduct urine pregnancy test on all female subjects of child bearing potential. Record method of contraception, as applicable, on source only.
6. Collect vital signs (blood pressure and pulse rate), height and weight.
7. Perform a physical examination (HEENT, lungs, heart, abdomen, skin, and neurologic).
8. Perform a 12-lead EKG.
9. Conduct clinical assessments:
  - a. Investigator is to identify a treatment area on the face and/or scalp (if not already done at screening).
  - b. Investigator is to document the number and location of the lesions with in the treatment area and on a grid foil. One copy of the grid foil should be inserted into the subject's source document and the other should be given to the subject for use at home.
  - c. Investigator is to count the visible and palpable AK lesions in treatment areas
  - d. Confirm size and location of selected treatment area on grid foil
10. Randomize subject by using IWRS.
11. Weigh and then dispense tubes of study product to subject. The tear-off panel from the box of the investigational products is to be affixed to the source document and filed in subject's chart. Instruct subject on study product use. Review the Subject Instructions with the subject.
12. When the subject performs the first application of study product at the site, ensure that it is done correctly.
13. Remind subject to bring all tubes of study product to next visit.
14. Dispense and review use of diary. Remind subject to report missed applications and/or potential AEs as well as any medication used in the diary and to bring diary to each visit.
15. Schedule next visit.
16. Complete eCRF for randomized subjects. For every screen failure subject, record the subject number, date of visit, date of consent, reason for screen failure, and study status (screen failure) in the eCRF.

